## **Study protocol**

*The conventional group* received washing oneself and dressing training from the same OT in the occupational therapy unit for 3 days. On the 4th day of training, the OT supervised the patients while performing these tasks in the rehabilitation ward. After that, a nursing staff took responsibility for these activities in a traditional way of nursing care until day 14. Duration of training session was one hour per day.

*The experimental group* received the new “seamless self-care training” technique, which was characterized by a collaboration between OTs and nurses. The training team consisted of two OTs with standardized training skills according to the self-care checklist for dressing and washing oneself (see appendix). The patients received training in the occupational therapy unit for 2 days and then were supervised by OTs at the rehabilitation ward for the next 2 days. On the 4th day of the training, one nursing staff came along with the OT in order to learn how to facilitate the patients according to their abilities to carry out these tasks. After that, the patients received further training from the nursing staff until day 14. Duration of training session was one hour per day. In this group, the nursing staff guided the patients to perform dressing and washing oneself according to the self-care checklist for dressing and washing oneself.

In both groups, each patient was in contact with and trained by only one OT and one nurse throughout the period of the study.

In order to reduce cross-contamination of the training techniques, each technique was delivered in separate periods of time. We first finished collecting data in the conventional group for one month and then conduct the seamless self-care training technique with the experimental group. During the study, patients received physical therapy or other treatments that did not affect dressing and washing oneself abilities.

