### *Outcome measurement*

For the main outcome, patients' abilities in dressing and washing oneself were evaluated by another OT on day 1 and day 14 of the program in both groups. However, since there were no specific detailed measurements for assessing such abilities after a stroke, the authors developed steps of dressing and washing oneself, so called “Self-care checklist for dressing and washing oneself”. Based on task analysis, these two self-care activities consisted of 5 sequential activities: taking off a shirt, taking off pants, washing oneself, putting on a shirt and putting on pants. Each activity was composed of 4 steps, so there were 20 steps in total. Each step could be scored as 0, 1, or 2. A score of 2 meant the patients could perform the task independently, while 1 meant the patients could do the task with verbal cueing, and 0 meant the patients could not perform the task within 5 minutes or needed assistance to complete the task. Therefore, the maximum score was 40 for the independent performance measurements of dressing and washing oneself. This checklist had a high correlation with the Modified Barthel Index as analyzed with Spearman's correlation  $r = 0.764$ ,  $p < 0.001$ .

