## **Statistical analysis plan**

Demographic and clinical variables were summarized using descriptive statistics. Continuous variables were described as mean with standard deviation (SD) and median with an interquartile range (IQR). Categorical variables were described by frequency and percentage. Statistical data analysis was performed using SPSS, Version 18.0, and a p-value of 0.05 was considered to be statistically significant. The differences in the outcome of self-care training and self-efficacy

between the two groups were analyzed by independent t-test, or within group by paired t-test, while differences between groups covariate by day 1 were analyzed by analysis of covariance (ANCOVA). The gain level was analyzed by chi-square test for assessing trends.

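### Does a main outcome total that gives half credit for cued steps misstate independence, given that the experimental group's nurses worked from the same checklist?

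*Combined protocol and SAP*

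**What the plan says.** Outcome measurement defines the main outcome as the patient's ability at dressing and washing, assessed on day 1 and day 14 in both groups by an OT other than the training OT. The checklist has five activities of four steps. "Each step could be scored as 0, 1, or 2". A score of 2 is independent performance, "while 1 meant the patients could do the task with verbal cueing", and 0 is failure within five minutes or a need for assistance. The section then says: "Therefore, the maximum score was 40 for the independent performance measurements of dressing and washing oneself". It also reports a Spearman correlation of 0.764 between the checklist and the Modified Barthel Index.

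The Study protocol section describes the two nursing phases. In the conventional group a nurse "took responsibility for these activities in a traditional way of nursing care until day 14". In the experimental group a nurse joined the OT on the fourth day to "learn how to facilitate the patients according to their abilities to carry out these tasks", and afterwards "the nursing staff guided the patients to perform dressing and washing oneself according to the self-care checklist for dressing and washing oneself". The two techniques were kept apart in time: "In order to reduce cross-contamination of the training techniques, each technique was delivered in separate periods of time".

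The Statistical analysis plan lists an independent t-test, a paired t-test, an ANCOVA with the day 1 value as covariate, and a chi-square test for trend on a gain level that it does not define. It states no analysis of the steps scored 2 alone.

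**The concern.** Three facts, read together, suggest a problem. The total carries the label of independent performance, yet a cued step earns half the points of an independent one. One group's nurses worked from the very list that is scored, while the other group's nurses did not. And no stated analysis separates a gain from 0 to 1 from a gain from 1 to 2.

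If the experimental programme mainly taught patients to complete steps when prompted, its total would rise while patients still needed someone beside them. A report calling that a gain in independence would claim more than the data show. Adjusting the day 14 total for the day 1 total would not reveal it, because the split is lost when the steps are summed.

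**Working it through.** **Inputs** (all from Outcome measurement): 5 activities, 4 steps each, step scores 0, 1 or 2.

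**The plan's own figure.** 5 × 4 = 20 steps, and 20 × 2 = 40. The stated maximum is reproduced.

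**What a total leaves open.** Let n2 be the number of steps scored 2 and n1 the number scored 1. Then T = 2·n2 + n1, with n2 + n1 at most 20. For a given T, n2 lies between max(0, T − 20) and the integer part of T/2:

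| Total T | Fewest independent steps | Most independent steps |
|---|---|---|
| 10 | 0 | 5 |
| 20 | 0 | 10 |
| 30 | 10 | 15 |
| 38 | 18 | 19 |
| 39 | 19 | 19 |
| 40 | 20 | 20 |

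So the arithmetic behind the worry is right. A patient cued on all 20 steps scores 20, as does a patient with 10 independent and 10 failed steps. These are limits set by the scoring. They are not estimates of what occurred, and the documents give no step-level data that would make the extremes likely.

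**What the total measures.** The same sum can be written T = (n1 + n2) + n2: the number of steps done without assistance beyond a verbal cue, plus the number done independently. Each independent step counts in both terms, so it earns twice the credit of a cued one. That is a graded ability score, which is what the section says the main outcome is. The phrase about independence appears once, attached to the maximum of 40. At that value n2 must be 20, so the phrase is accurate there.

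**Whether the group comparison is biased.** The difference in mean totals equals 2 × (difference in mean n2) + (difference in mean n1). If the programmes lead to the same distribution of step scores, both terms are zero whatever the weights. The half credit therefore cannot create a difference by itself. It would distort the comparison only if the scoring were applied differently by group, and the plan applies one rule to both groups on both days. Guidance in a training session is also not cueing at the assessment: a step prompted in training scores 2 on day 14 if the patient then does it unaided.

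**Whether the overlap with the checklist is a flaw.** Side by side, the two descriptions in the Study protocol section have the same nurse-led span, from day 5 to day 14 (14 − 4 = 10 days), and the same stated session length of one hour per day. What differs is how the nurse works: by the checklist or in the traditional way. That difference is the intervention, and dressing and washing are the skills it targets. Nothing in the text says that guidance took the form of verbal cueing, or that it would produce 1s rather than 2s.

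**What a separate count would add.** A count of steps scored 2 uses the same 20 steps, so it leaves the overlap between training and checklist as it is. It also ignores real progress: 10 steps moving from 0 to 1 raise the total by 10 points (10/40 = 25% of the maximum) and the count by 0.

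**The case for a change.** The strongest reply is that this is more than the usual loss of detail in a summed scale. One group practised the scored steps with a nurse, the total is given an independence label, and two patients can be ranked in opposite order by total and by independent steps. A patient at 20 with no independent step is 4 points ahead of a patient at 16 with 8. The correlation of 0.764 with the Modified Barthel Index supports the total as a measure of ability but does not show at which level a group difference lies. A table and one supportive ANCOVA would cost little.

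Part of this stands. The total alone cannot show how much of a difference is independent performance, and a report should not say more than that. The gain level is undefined, so it cannot be assumed to fill the gap; equally, it cannot be assumed not to. But the reversal is a single extreme pattern, and nothing in the documents suggests that it occurred. The step from practising the scored tasks to inflating cued scores is an inference that the text does not supply. Even on that reading, a higher total is a real gain in the trained tasks. The extra analysis would leave the main outcome and its test as they are, and it depends on step scores having been kept, which the documents do not say.

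**Conclusion.** The concern does not hold. The plan defines the outcome as ability, discloses that a cued step scores 1, and scores both groups by the same rule on both days with a separate OT as assessor. The half credit produces no spurious difference between groups, and checklist-guided nursing is the contrast the study sets out to test. The ambiguity is real but ordinary: it is widest at a total of 20 (0 to 10 independent steps) and gone at 39 and 40. It limits how finely a difference can be described and does not affect whether the comparison of totals is valid. A table of steps scored 0, 1 and 2 by group and day would be informative, but that is a reporting choice.

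This rests on two assumptions: that the assessor applied the stated scoring alike in both groups, and that the checklist appendix, which is not in the text available, agrees with the scoring described. The sequential periods and the unstated blinding of the assessor are separate matters, and this conclusion says nothing about them.

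### Each technique has its own period, so the group contrast estimates technique and period combined; the plan neither says so nor names one main between-group estimate

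*Combined protocol and SAP*

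**What the plan says.** The Study protocol section gives the order of data collection: "We first finished collecting data in the conventional group for one month and then conduct the seamless self-care training technique with the experimental group". It also gives the reason: "In order to reduce cross-contamination of the training techniques, each technique was delivered in separate periods of time". On other care it states: "During the study, patients received physical therapy or other treatments that did not affect dressing and washing oneself abilities". It adds that every patient, in either group, worked with a single OT and a single nurse. In the Outcome measurement section, dressing and washing ability is the main outcome, scored from 0 to 40, and patients "were evaluated by another OT on day 1 and day 14 of the program in both groups".

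In the Statistical analysis plan, "a p-value of 0.05 was considered to be statistically significant". Differences in outcome "between the two groups were analyzed by independent t-test", and "differences between groups covariate by day 1 were analyzed by analysis of covariance (ANCOVA". A further line reads: "The gain level was analyzed by chi-square test for assessing trends". The t-test is not tied to day-14 or change scores, and gain level is not defined. Day 1 is the only covariate named. The tests are not ranked, no confidence interval is mentioned, and nothing is said about period when interpreting the result.

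**The concern.** With one technique per period, anything that differed between the periods (ward routine, staff, scoring habits, case mix) enters the group difference together with the technique. The two safeguards help but do not close the gap. The statement about other treatments is an assertion, with no measurement or adjustment described. Using an assessor other than the trainer does not establish that scoring was the same in both periods. ANCOVA on day 1 deals only with what shows in the day-1 score.

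There is a second, related gap. The t-test and the ANCOVA answer the between-group question differently and respond differently to a period shift. If either may carry the conclusion, the nominal 5% does not hold even without a shift. What is at stake is the study's central conclusion: a p-value below 0.05 could be reported as an effect of the seamless technique alone, from whichever test reached it.

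**Working it through.** **Inputs from the documents.** One technique per period; main outcome on day 1 and day 14; significance level 0.05 (sidedness not stated, two-sided assumed); the tests listed above. No sample size or power figure is given to reproduce. The one derived figure, the checklist maximum, checks: 5 activities × 4 steps × 2 points = 40.

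**Assumed inputs.** 30 per group (10 to 40 shown where useful); SD 1 on both days; day-1/day-14 correlation ρ of 0.5 to 0.7; true technique effect 0; period shift 0, 0.1 or 0.3 SD; normal data. If the checklist SD were 8 to 12 points, 0.3 SD would be 0.3 × 8 = 2.4 to 0.3 × 12 = 3.6 points.

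**Step 1: can technique and period be separated?** Write the day-14 mean as a + b·(day 1) + τ·technique + π·period. Here technique and period take the same value for every patient, so only τ + π is estimable. A design matrix with intercept, day 1, technique and period has 4 columns and rank 3.

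**Step 2: no effect and no shift, 30 per group.** The day-14 t-test and the ANCOVA each reject in about 5% of trials. The chance that at least one does (200,000 simulated trials per setting) is 7.3% at ρ = 0.5 and 8.3% at ρ = 0.7.

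**Step 3: day-14 t-test with a period shift δ.** The noncentrality is δ√(n/2) with 2n − 2 degrees of freedom.
- δ = 0.3, n = 30: 0.3 × √15 = 1.162, rejection 20.8%
- δ = 0.3, n = 10: 0.3 × √5 = 0.671, rejection 9.7%
- δ = 0.3, n = 20 and n = 40: 15.2% and 26.3%
- δ = 0.1, n = 30: 0.1 × √15 = 0.387, rejection 6.7%

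**Step 4: ANCOVA.** The bias is (shift on day 14) − ρ × (shift on day 1).
- Equal shift of 0.3: 0.3 × (1 − 0.5) = 0.15 SD, or 0.3 × (1 − 0.7) = 0.09 SD
- Shift of 0.3 after day 1 only: 0.30 SD at either correlation

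**Step 5: t-test on change, if that is what is meant.** An equal shift cancels. A later shift stays in full, against an SD of change of √(2(1 − ρ)): 1.00 at ρ = 0.5 and 0.775 at ρ = 0.7.

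Rejection at n = 30 with a 0.3 SD shift and no technique effect:

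| Analysis | Equal on both days | After day 1 only |
|---|---|---|
| Day-14 t-test | 21% | 21% |
| ANCOVA, ρ = 0.7 / 0.5 | 8% / 10% | 35% / 26% |
| Change-score t-test, ρ = 0.7 / 0.5 | 5% / 5% | 31% / 21% |

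None of these three tests protects in both columns. ANCOVA is the most sensitive to a later shift because it is the most precise. The chi-square trend test was not evaluated, because gain level is undefined.

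**The case against.** The strongest reply is that this is an openly stated trade-off with a sensible reason, and that no error has been shown. The plan never says that p < 0.05 will be credited to the technique; it only defines significance and lists comparisons. A limit on interpretation could go in the report's discussion. The plan already contains the day-1 ANCOVA, and the single OT and nurse per patient limit staff variation within a patient. Much of this stands. A reader might infer that the design is hidden or invalid, or that the plan makes a causal claim; the text supports neither.

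A reader might also infer that the comparison is biased, or that it shows only a difference between periods. The documents show no shift or case-mix difference, and the contrast contains any technique effect as well as any period effect. A smooth calendar-date trend is not perfectly aliased with group, but separating it would be imprecise and would rest on assumptions about its form.

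The magnitudes are wholly assumed. A 0.3 SD shift between consecutive periods has no support in the text, milder cases give 7 to 10%, and the calculation ignores the 0 to 40 bounds. The plan is written mostly in the past tense, so a choice of main analysis made now may not be prospective.

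These points do not answer the aliasing or the absence of a main estimate. Both follow from the text and do not depend on any assumed number.

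**Conclusion.** The concern holds in a limited form. The planned between-group contrasts estimate technique and period combined. The Statistical analysis plan does not say this, does not name a main contrast, and adjusts for no baseline factor other than day 1. This rests on the Study protocol, Outcome measurement and Statistical analysis plan sections, and confidence in it is high.

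The size is not known. Under the stated assumptions, the free choice between the day-14 t-test and ANCOVA costs about 2 to 3 percentage points above the nominal 5% when there is no shift. With a 0.3 SD shift, the false-positive rate for the technique runs from 8% to 35% across those two analyses at 30 per group. These rates show how the result depends on the test and on the timing of a shift; they do not estimate bias in this trial. The study remains usable, but the gap should be fixed because it determines what a significant result may be said to mean.

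**What to change.** 1. Name the already planned ANCOVA of the day-14 score on group and day-1 score, with its 95% confidence interval, as the single main between-group estimate. Make the t-test secondary and state whether it uses day-14 or change scores.
2. State in the plan and the report that, because the groups are not concurrent, this estimate reflects technique and period combined, and that p < 0.05 is not attributed to the technique alone.
3. Optionally, as a sensitivity analysis, add a short list of baseline prognostic variables from those already summarised, fixed before outcomes are examined. An open-ended choice would add analytic freedom.

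If outcomes have already been seen, label both the choice of main analysis and any added covariates post hoc.

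The cost is wording, a few degrees of freedom if covariates are added, and a more cautious conclusion. The sequential delivery and its contamination safeguard stay as they are. Item 1 settles which test counts, but it does not remove a shift arising after day 1, and there ANCOVA rejects more often than the day-14 t-test. Item 2 is therefore needed alongside it.

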### *Outcome measurement*

For the main outcome, patients' abilities in dressing and washing oneself were evaluated by another OT on day 1 and day 14 of the program in both groups. However, since there were no specific detailed measurements for assessing such abilities after a stroke, the authors developed steps of dressing and washing oneself, so called “Self-care checklist for dressing and washing oneself”. Based on task analysis, these two self-care activities consisted of 5 sequential activities: taking off a shirt, taking off pants, washing oneself, putting on a shirt and putting on pants. Each activity was composed of 4 steps, so there were 20 steps in total. Each step could be scored as 0, 1, or 2. A score of 2 meant the patients could perform the task independently, while 1 meant the patients could do the task with verbal cueing, and 0 meant the patients could not perform the task within 5 minutes or needed assistance to complete the task. Therefore, the maximum score was 40 for the independent performance measurements of dressing and washing oneself. This checklist had a high correlation with the Modified Barthel Index as analyzed with Spearman's correlation  $r = 0.764$ ,  $p < 0.001$ .

## **Statistical analysis plan**

Demographic and clinical variables were summarized using descriptive statistics. Continuous variables were described as mean with standard deviation (SD) and median with an interquartile range (IQR). Categorical variables were described by frequency and percentage. Statistical data analysis was performed using SPSS, Version 18.0, and a p-value of 0.05 was considered to be statistically significant. The differences in the outcome of self-care training and self-efficacy

between the two groups were analyzed by independent t-test, or within group by paired t-test, while differences between groups covariate by day 1 were analyzed by analysis of covariance (ANCOVA). The gain level was analyzed by chi-square test for assessing trends.

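### The main between-group comparison has two tests at 0.05, an unadjusted t-test and a day-1-adjusted ANCOVA, and no rule for which one decides

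*Combined protocol and SAP*

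**What the plan says.** The section Outcome measurement names one main outcome and its two time points: "For the main outcome, patients' abilities in dressing and washing oneself were evaluated by another OT on day 1 and day 14". It also sets the ceiling of the scale: "Therefore, the maximum score was 40 for the independent performance measurements of dressing and washing oneself". It attaches no test to this outcome.

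The Statistical analysis plan gives one threshold for everything: "a p-value of 0.05 was considered to be statistically significant". One sentence then covers both outcomes, beginning "The differences in the outcome of self-care training and self-efficacy" and continuing "between the two groups were analyzed by independent t-test, or within group by paired t-test, while differences between groups covariate by day 1"; the last of these is assigned to ANCOVA. A further test follows: "The gain level was analyzed by chi-square test for assessing trends".

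No test is called primary or supportive, none is conditional on another, and the level is not split.

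The section Study protocol describes the order of the groups: "We first finished collecting data in the conventional group for one month and then conduct the seamless self-care training technique with the experimental group".

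**The concern.** The main question, whether the two techniques differ on the checklist score, has two between-group tests at the same level and no stated decider. The variable for the t-test is also open: it could be the day-14 score or the change from day 1.

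This matters in three ways. If significance on either test may carry the conclusion, the false-positive rate is above 5%. If a day-14 t-test carries it, the conclusion rests on the test that usually has less power. That test also passes any day-1 difference into the result, whereas ANCOVA removes the part that the day-1 score captures. Because the groups ran one after the other, concurrent allocation does not secure day-1 balance.

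**Working it through.** **Inputs from the documents.** Threshold 0.05; main outcome on days 1 and 14; score from 0 to 40; successive periods. No sample size, power, SD, correlation or baseline data are given, so there is no design figure to reproduce and what follows is illustration.

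**Assumed.** 20–40 patients per group (n); day-1/day-14 correlation r of 0.5–0.8; two-sided 0.05; normal scores with equal SD; t-test on the day-14 score unless stated. Figures in square brackets repeat the settings with whole-number scores cut at 0 and 40 (underlying mean 12 on day 1 and 28 or 36 on day 14, SD 12; about 17–53% of patients at 40 on day 14). Simulations used 40,000 trials per setting for normal scores and 20,000 for bounded scores.

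**Step 1: no effect, balanced groups.** In large samples, the correlation between the two test statistics is √(1 − r²) for the day-14 t-test with ANCOVA, and √((1 + r)/2) for the change t-test with ANCOVA. The chance that at least one exceeds 1.96 in absolute value follows from the bivariate normal distribution:

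| r | Day-14 t-test and ANCOVA: correlation | At least one significant | Change t-test and ANCOVA: correlation | At least one significant |
|---|---|---|---|---|
| 0.5 | 0.866 | 7.3% | 0.866 | 7.3% |
| 0.7 | 0.714 | 8.3% | 0.922 | 6.8% |
| 0.8 | 0.600 | 8.7% | 0.949 | 6.5% |

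The value for independent tests would be 1 − 0.95² = 9.75%. Simulation gives 7–9% [7–9%] with the day-14 t-test and 7% [7–8%] with the change t-test. The two tests differ on significance in 4–8% [4–7%] and 3–5% [3–6%] of trials respectively.

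**Step 2: no effect, a day-1 gap of d SD.** Two cases bracket what the gap might do.

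- *It regresses linearly.* The expected day-14 gap is r·d, which shifts the t statistic by r·d/√(2/n). For d = 0.4, n = 20, r = 0.5: 0.20/0.316 = 0.63, about 10% rejection. For n = 40, r = 0.8: 0.32/0.224 = 1.43, about 30%. The simulated values are 9% and 29%. ANCOVA is unbiased here.
- *It persists unchanged.* The day-14 gap is d. The exact noncentral-t rejection rate for d = 0.4 is 23.4%, 33.2% and 42.4% at n = 20, 30 and 40. ANCOVA removes only r·d and keeps (1 − r)·d, which is 0.20 SD at r = 0.5 and 0.08 SD at r = 0.8. A comparison of gain is unbiased here.

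False-positive rates over n = 20–40:

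| Gap | Day-14 t-test | ANCOVA | t-test on gain |
|---|---|---|---|
| 0.2 SD, regresses | 6–11% [6–10%] | 5% [5%] | 5–7% [6–9%] |
| 0.4 SD, regresses | 9–29% [8–28%] | 5% [5%] | 7–14% [8–22%] |
| 0.2 SD, persists | 9–14% [8–14%] | 5–8% [5–8%] | 5% [5–7%] |
| 0.4 SD, persists | 23–42% [19–40%] | 7–17% [6–16%] | 5% [5–13%] |

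**Step 3: true effect of 0.6 SD, 30 per group.** Power when balanced: day-14 t-test 63% [50–59%], ANCOVA 74–96% [57–86%], t-test on gain 63–95% [30–77%].

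The day-14 t-test and ANCOVA differ on significance as follows:

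| Day-1 position of the experimental group | 30 per group | 20–40 per group, normal scores |
|---|---|---|
| Balanced | 18–35% [14–32%] | 14–44% |
| 0.2 SD lower | 28–57% [20–50%] | 24–59% |
| 0.2 SD higher | 14–17% [14–20%] | 8–29% |

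In the balanced case at 30 per group, ANCOVA alone is significant in 14–34% of trials and the t-test alone in 0.5–3% (about 12–42% and 0.1–4% over 20–40 per group). Both tests significant in opposite directions occurs in under 0.05% of trials in every setting.

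**The case against.** The sentence reads naturally as an unadjusted comparison followed by a baseline-adjusted one, so the gap may be no more than a missing label. The direct cost is small: 7–9% instead of 5%, and only if either test may carry the conclusion, a rule the plan does not state. The larger error rates need an assumed day-1 gap and a conclusion resting on the day-14 t-test, so they belong partly to the successive-period design. Most of the disagreement under a true effect is ANCOVA finding what the t-test misses. The choice of ANCOVA over gain is also not settled by the documents, since it depends on whether a gap would regress or persist.

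Much of this stands, and it limits the size of the point. The 7–9% is the cost of the missing rule itself; the gap figures show what is at risk if the t-test is taken as decisive. But the natural reading fixes an order of reporting only. It does not say which result counts when the two disagree, and nothing in the plan prevents the unadjusted test from being the one that counts. The doubt about gain is met by reporting it as a sensitivity analysis.

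**Conclusion.** The concern holds and should be fixed. It is certain from the text that two between-group tests share one threshold without a stated decider, and that the t-test variable is undefined. The size is illustrative, because sample size, correlation and any day-1 gap are all assumed. On those assumptions the error inflation from choosing between the tests is modest. The more serious exposure is a conclusion resting on the day-14 t-test, which in these settings has less power than ANCOVA and is more affected by a day-1 gap of either kind. Confidence is high in the observation. It is lower in ANCOVA as the best estimator in every case, since ANCOVA can exceed 5% if a gap persists.

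**What to change.** In the Statistical analysis plan:

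- Name the ANCOVA of the day-14 checklist score on group, with the day-1 score as covariate, as the single deciding analysis of the main outcome. Report the adjusted difference with its 95% confidence interval.
- Label the unadjusted t-test and the gain-level trend test supportive, and state which variable the t-test uses.
- Report the between-group comparison of gain as a sensitivity analysis. Note that it holds about 5% if a baseline gap would simply persist, but not if many patients reach 40.
- Do not use the within-group paired tests to compare the techniques.
- State that ANCOVA does not remove period effects beyond the day-1 score.
- Say how the same pair of tests is to be read for self-efficacy, which shares the sentence.
- If results have been seen, date and disclose the change and report all the analyses.

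The cost is a few sentences. The ANCOVA is already planned and needs no new data. The drawbacks are that it corrects only for the day-1 score, and that naming it late does not restore prespecification.

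### Groups are formed by sequential period, yet the between-group tests adjust for nothing or only for the day-1 score, so any difference in prognostic mix between periods could pass as a technique effect

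*Combined protocol and SAP*

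**What the plan says.** Under Study protocol, the reason for separating the groups in time is given as "In order to reduce cross-contamination of the training techniques, each technique was delivered in separate periods of time". The order is then fixed: "We first finished collecting data in the conventional group for one month and then conduct the seamless self-care training technique with the experimental group". The available text describes no randomisation, matching or concurrent control. Only the conventional period has a stated length.

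Under Outcome measurement, ability is "evaluated by another OT on day 1 and day 14 of the program in both groups", and "the maximum score was 40 for the independent performance measurements of dressing and washing oneself".

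The Statistical analysis plan gives two between-group methods. Differences "between the two groups were analyzed by independent t-test, or within group by paired t-test", and "differences between groups covariate by day 1 were analyzed by analysis of covariance (ANCOVA". It does not say which of the two carries the conclusion. Other patient characteristics have one stated use: "Demographic and clinical variables were summarized using descriptive statistics". The variables are not listed. The significance level is given as "a p-value of 0.05 was considered to be statistically significant", without saying whether tests are one- or two-sided.

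**The concern.** In a randomised trial, a prognostic factor left out of the model adds noise but no systematic difference between groups. Here the groups are consecutive intakes, so the design does not guarantee that they are alike. The only protection is the day-1 covariate in the ANCOVA, and the t-test lacks even that.

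The day-1 score is not enough when the outcome is recovery after stroke. Take two patients with the same day-1 score, one early after stroke and still improving, the other later and stable. They have different expected day-14 scores whichever technique they receive. If one period holds more of the first kind, the group coefficient absorbs the difference. The bias could favour either technique, depending on which intake was nearer to stroke onset. The Study protocol's one remark on outside influences concerns other treatments, not patient mix or spontaneous recovery.

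At stake is whether a significant group difference can be read as an effect of the technique.

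**Working it through.** **What can be reproduced.** The documents give no sample size, SD, expected effect or power, so there is no design figure to check. The maximum score agrees with its components: 5 activities × 4 steps × 2 points = 40. Everything below is illustration.

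**Assumed inputs (none from the documents).** No true technique effect. Each extra week since stroke lowers the 14-day gain by s = 0.5 or 1 point. SD of weeks since stroke 2, residual SD 5, 20 or 30 patients per group, two-sided 0.05. Weeks since stroke is unrelated to the day-1 score. The mean shift between groups is d = 0, 1 or 2 weeks.

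**Day-1-only ANCOVA.**
- False difference = s × d.
- Residual SD with stage left out = √(5² + s² × 2²), which is √26 = 5.10 for s = 0.5 and √29 = 5.39 for s = 1.
- SE of the group difference ≈ residual SD × √(2/n).
- Rejection rate from the non-central t distribution with 2n − 3 degrees of freedom and non-centrality (s × d)/SE.

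| n per group | s | d (weeks) | False difference (points) | SE | Ratio | Rejection |
|---|---|---|---|---|---|---|
| 20 or 30 | either | 0 | 0 | – | 0 | 5% |
| 20 | 0.5 | 1 | 0.5 | 1.61 | 0.31 | 6% |
| 20 | 1 | 2 | 2.0 | 1.70 | 1.17 | 21% |
| 30 | 0.5 | 1 | 0.5 | 1.32 | 0.38 | 7% |
| 30 | 1 | 2 | 2.0 | 1.39 | 1.44 | 29% |

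Simulation of the same model, 4,000 trials per setting, agrees: about 6% to 20% at 20 per group and 6% to 30% at 30 per group. Adding weeks since stroke brings the mean difference to within 0.05 points of zero and the rate to about 5%.

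**A second set of assumptions, in SD units.** Day-1 coefficient 0.6; recovery stage correlated 0.2 with the day-1 score and worth a further 0.3 or 0.5 SD of day-14 score per SD of stage; groups 0.5 SD apart in stage with equal day-1 means. Day-1-only ANCOVA shows a false effect of about 0.15 to 0.25 SD. It rejects in 9% to 20% of trials at 20 per group, 14% to 34% at 40 and 18% to 47% at 60. The unadjusted t-test carries the same bias. With no stage difference, all the models hold about 5%. The rate rises with sample size because the bias stays fixed while the SE shrinks.

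**What adjustment cannot do.** Give every later patient a pure period effect of 0.3 SD, with stage balanced. The model with both day-1 score and stage still estimates about 0.30 SD and rejects in 25%, 48% and 66% of trials at 20, 40 and 60 per group.

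**The case against.** The strongest reply is that nothing shows the two intakes differ. If adjacent periods on the same ward draw on the same population, any imbalance is chance, and the day-1 ANCOVA is unbiased on average and holds about 5%. With an SD of 2 weeks, the chance SE of the group difference in time since stroke is 2 × √(2/20) = 0.63 weeks, or 2 × √(2/30) = 0.52. A 1-week shift is then 1.6 to 1.9 standard errors and a 2-week shift 3.2 to 3.9. The upper rates therefore need a strong systematic shift, which nothing in the documents suggests. This stands: a reader might infer that the comparison is biased, and the documents do not support that. They support only that it is unprotected.

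The illustration also favours its own remedy. The confounder is linear, measured without error and identical to the covariate added, so the bias vanishes by construction. The day-1 score recovers none of the stage shift in either set of assumptions, and the ceiling at 40 is ignored. This stands too; real adjustment would be less complete.

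A reader might further infer that time since stroke was recorded and simply left unused, or was never recorded. Neither is shown, because the clinical variables are not listed. Eligibility criteria are not in the text available for review, so a narrow time window that would shrink the problem cannot be excluded.

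Finally, period effects such as staff, learning or ward changes may matter more than patient mix, and an adjusted p-value could give false comfort. That is a reason to state the limit plainly. It is not a reason to leave measured patient mix unadjusted.

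**Conclusion.** The concern holds in conditional form. It is certain from the text that groups follow period, that one between-group test is unadjusted, that the other adjusts for day 1 alone, and that other patient characteristics are only described. Whether prognosis differed between periods is unknown, so the size of any bias is unknown as well.

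Under the assumptions on the points scale, a 1 to 2 week shift yields a false difference of 0.5 to 2.0 points and a false-positive rate of about 6% to 30%. The low end is close to nominal, and with no shift the rate is about 5%. These figures show what could happen; they are not evidence about this trial.

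The opposite over-reading should also be avoided: a reader might infer that the added covariates would make this a comparison of techniques alone. They would not, because period and technique coincide completely.

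**What to change.** In the Statistical analysis plan:

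1. Name as the main between-group analysis an ANCOVA of the day-14 score on group, day-1 score, time since stroke and age. Take time since stroke from the chart if it is not already recorded. This model replaces the unadjusted t-test as the basis for the conclusion.
2. Report the day-1-only ANCOVA beside it, with both estimates and confidence intervals, so that the reader can see how far the result depends on patient mix.
3. Fix the covariate list before outcomes are seen. The document is written largely in the past tense, so if data have already been seen, label the adjusted model as added afterwards.
4. State that adjustment addresses only measured patient mix, that period effects remain fully aliased with technique, and that the result is a non-randomised sequential comparison.

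The cost is one degree of freedom per covariate (with 20 per group, from 40 − 3 = 37 to 40 − 5 = 35), one more model in the SPSS software already planned, and possibly some chart extraction.
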